7.4. Criterion of withdrawal and final data matrix

The data will be included in the final matrix for the analysis to those who have complied with the guidelines throughout the field work; in accordance with exclusion criteria. The following lost data are considered:

- No possibility of intravenous catheterization in the first period of the bioequivalence study.
- Subject that does not attend the second period.
-

It is not considered lost data when in the second period an intravenous cannulation is not possible but it has been tried at least once. It is possible to collect all the data required by this study for analysis of the primary variable; which is for which the individuals calculated in the sample size are required.

That is, only the data not lost or deviations from the protocol will be included; analysis for protocol compliance

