8.5. Adherence to interventions and protocol deviations

Adherence to the protocol will be ensured with the following resources:

- The time and the power of the heat source emitted to the carob bean sacks will be carried out by means of a microwave, whose power and time will be pre-set.

- The application time of the seed bags, seven minutes, will be controlled through a portable countdown timer. There will be a countdown and ascending timer with CE marking, for each subject. The nurse will program the device so that, after seven minutes from the application of the bags, an alarm is issued to remove them. Likewise, when the alarm sounds, an ascending count begins and the time elapsed in excess can be known; in which case.

Deviations from the protocol and data retrieved will be considered in the following cases:

Application of dry topical heat

1. If the two sacks of seeds are not heated sufficiently -> It will proceed to heat two more again. There will always be two more sacks of reserve; so reheating sacks is not recommended because the temperature that could reach them is unknown and could generate "noise" to assess the effectiveness of the intervention.
2. If 7 minutes are not reached -> Protocol deviation
3. If the bags are left in excess of 7 minutes -> Protocol deviation
4. If a sack of seeds is released, or both, and recovers to its previous position in less than 1 minute (Flexibility time). No need to let act one more minute -> Data recovered.
5. If a sack of seeds, or both, comes off and does not recover to its previous position in less than 1 minute (Flexibility time) -> Protocol deviation
6. If the two sacks of seeds were detached, without the possibility of estimating the time that has elapsed approximately -> It is recovered and the process is started again.

There will be another pair of bags for the possibility of loss of them.

Application of high tourniquet pressure

1. Pressure exerted with the sphygmomanometer less than 100 mmHg is considered insufficient -> Protocol deviation
2. If the pressure of the sphygmomanometer gradually decreases due to forgetfulness of the valve fixing that controls the air output before performing venipuncture-> fix the valve. Data recovered.
3. If the pressure of the sphygmomanometer gradually decreases due to forgetfulness of the valve fixing that controls the air output after performing venipuncture-> Protocol deviation

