11. SAFETY ASSESSMENT

11.2. Safety monitoring

11.2.1. Record adverse events

A record of the secondary events and the symptomatic and specific adverse reactions will be carried out, which will be assessed by visual inspection. It will be the nurses, who apply each arm, those responsible for the visual inspection and the communication of the adverse reaction, if any, to the principal investigator and / or collaborating researcher. Both the principal investigator, the collaborating researcher and the collaborating nurses will be able to record any secondary effect (9).

The definition of adverse reactions requires adaptation to medical devices. Its calving is considered from the application of any intervention and / or comparator. There will be an approximation of the causality between the effect and the applied method; according to what the World Health Organization establishes (WHO) (56):

1. Certain
2. Probable.
3. Possible.
4. Unlikely
5. Conditional / Not classified
6. Not evaluable / Unclassifiable

Likewise, the severity will be recorded; according to the WHO (57), with modification:

1. Serious
2. Moderate.
3. Mild.
4. Incidental.

The frequency of appearance thereof will be calculated according to what is established by the Council for International Organizations of Medical Sciences (CIOMS) (58):

1. Very common: They occur with a frequency greater than or equal to 1 case every 10 patients.
2. Frequent: They occur with a frequency greater than or equal to 1/100 but less than 1/10.
3. Uncommon: They occur with a frequency greater than or equal to 1 / 1,000 but less than 1/100.
4. Rare: They occur with a frequency greater than or equal to 1 / 10,000 but less than 1/1000.
5. Very rare: They occur with a frequency less than 1 / 10,000.

Each case will be followed until it ceases, and the method used to remit said effect will be registered.

The appearance of local erythema has been registered as an adverse effect of dry topical heat (37). Likewise, the appearance of a hematoma due to traumatic puncture is expected.

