14.3. Secondary analysis attached

It has been considered that the approach of non-main secondary objectives could be carried out through the following methodology:

To identify the effectiveness of all the methods used in antebrachial venipuncture, in what refers to venipuncture at the first attempt.

It is intended to be addressed by means of a logistic regression, at the same time as the multivariate statistics for the main variable.

To evaluate the intensity of hemolysis of the blood samples, in what refers to the applied method, respectively.

It is considered that there is enough information on this subject to use a parametric test. In this case, the intensity of hemolysis is the dependent variable, it is considered justified to use an ANOVA test of a block test.

Identify the frequency of successful venipuncture at the first attempt and analyze if there is an association between it and the demographic characteristics of the individuals.

It is intended to be addressed through descriptive statistics. To analyze the association, a logistic regression will be performed; multivariate technique.

Analyze the correlation between methods used, intensity of hemolysis and pain.

It could be considered that enough information is known about pain to use parametric techniques, it is supposed to be the dependent variable and it is discrete. Therefore, it is intended to be approached using the ANOVA statistical technique or two-way F-test without interaction.

Identify and quantify adverse events, as well as their relation to skin types.

For the identification and quantification, a descriptive statistic will be carried out. In order to assess the possible association, using the Fitzpatrick scale, it is considered that there is not enough information about its distribution, so it is considered appropriate to use a nonparametric type test; the Kruskal-Wallis test.

14.4. Intermediate analysis.

Does not apply.

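### The compliers-only matrix in section 7.4 has no safety exemption, so adverse events recorded in lost or deviating subjects fall outside the planned adverse-event analyses

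*Combined protocol and SAP*

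**What the plan says.** Section 7.4 sets the membership of the analysis data: "The data will be included in the final matrix for the analysis to those who have complied with the guidelines throughout the field work". It names two kinds of lost data: "No possibility of intravenous catheterization in the first period of the bioequivalence study" and "Subject that does not attend the second period". One case is kept: "It is not considered lost data when in the second period an intravenous cannulation is not possible but it has been tried at least once". The section ends "That is, only the data not lost or deviations from the protocol will be included; analysis for protocol compliance". The grammar of that last sentence is loose. With the opening sentence and the closing reference to protocol compliance, the natural reading is that both lost data and deviations are excluded.

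Section 8.5 says what counts as a deviation, for example "If the bags are left in excess of 7 minutes -> Protocol deviation".

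Identifying and quantifying adverse events, and relating them to skin type, is a secondary objective (5.2.2). Section 11.2.1 has events recorded from the application of any intervention or comparator and followed until they cease. It then states: "The frequency of appearance thereof will be calculated according to what is established by the Council for International Organizations of Medical Sciences". Section 14.3 adds "For the identification and quantification, a descriptive statistic will be carried out" and a Kruskal-Wallis test for skin type. None of these sections names a safety population or an adverse-event denominator.

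**The concern.** A per-protocol set is a choice one can argue about for effectiveness. For safety it is the wrong base, because a subject is at risk once a method has been applied, whatever happens afterwards. Here some reasons for exclusion are tied to the reactions the protocol expects. Erythema is the registered effect of the heat, and heat beyond 7 minutes is a deviation. Haematoma is expected from traumatic puncture (11.2.1) and is linked to failed lines (9.8), and failure to cannulate in period 1 counts as lost data. A subject who does not return has already been exposed in period 1.

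What is at stake is a stated secondary objective, in a trial whose heat source carries no CE marking (3.3). If the data manager applies 7.4 literally, events that were properly recorded will not be counted.

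**Working it through.** **Inputs.** Section 6.3: five sets of twelve envelopes, so 60 subjects, 20 per intervention, half of each starting with the comparator. Section 14.1.2: paired success proportions 0.74 and 0.95, two-sided 5% alpha, 80% power, loss 0.12. Section 11.2.1: very common is at least 1/10; frequent is at least 1/100 and below 1/10. The documents do not give the within-subject discordance, any adverse-event counts or a deviation rate. These are assumed or left open below.

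**The plan's 60.** Under independence the discordant proportion is 0.74 × 0.05 + 0.95 × 0.26 = 0.284. The simple McNemar formula, (1.960 + 0.842)² × 0.284 / 0.21², gives 51 pairs, and 51 / 0.88 rounds up to 58. Connor's formula with continuity correction gives 59.97 after division by 0.88 when rounding is left to the end. At maximum discordance, 0.26 + 0.05 = 0.31, Connor's formula without correction gives 59.95. So 60 is reproduced within the choice of formula, and it is a number to enrol with losses included. The safety point does not depend on it.

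**Subjects leaving through loss.** 60 × 0.88 = 52.8, about 53 retained. Reading the allowance as 60 / 1.12 = 53.6 gives about 54. So 6 to 7 subjects leave. Both loss categories arise after a method has been applied in period 1, so these subjects were exposed. If losses spread evenly over sequences, about half of them received only the comparator, which is why the tables should go by method received. Deviations come on top.

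**Direction of the deviation exclusions.** Section 8.5 labels five situations a protocol deviation:

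| Situation | Exposure |
|---|---|
| Heat for less than 7 minutes | under |
| Heat for more than 7 minutes | over |
| Sack detached and not replaced within 1 minute | under |
| Cuff pressure below 100 mmHg | under |
| Cuff pressure falling after venipuncture, valve not fixed | under |

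Four of five are under-exposure. Removing those subjects could raise an event rate; removing the over-heated could lower it.

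**Size, with assumed event counts.**

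- 5 events among 53 retained: 5/53 = 9.4%, frequent. If 0, 1, 2 or all 7 of the dropped subjects had an event, the all-treated rate is 5/60 = 8.3%, 6/60 = 10.0%, 7/60 = 11.7% or 12/60 = 20.0%. The band becomes very common from one dropped event upward; with none, the rate falls.
- 0 events retained and 1 to 3 dropped: 0% in the matrix, against 1/60 = 1.7% to 3/60 = 5.0%.
- One intervention group: 2/20 = 10.0%, very common, becomes 1/19 = 5.3%, frequent, if one affected subject is excluded. This example sits exactly on the cut-off.
- Both heat groups together, if all 40 receive heat: 2/40 = 5.0% becomes 1/39 = 2.6%. Both are frequent.

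**Precision.** With no events, the one-sided 95% upper bound, 1 − 0.05^(1/n), is 5.5% at n = 53 and 4.9% at n = 60. The loss of precision is small. What matters is whose events are dropped.

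**The case against.** The strongest reply is that 7.4 was written for effectiveness. It justifies keeping period-2 failures by reference to the primary variable, and 11.2.1 describes recording and frequency without mentioning the matrix. Section 14.1.3.2.1 also defines cumulative incidence over the population at risk and mentions adverse reactions when justifying it. This has some weight, but the opening and closing sentences of 7.4 are general and no other analysis set exists. The cumulative-incidence formula is introduced for success and failure and does not override 7.4. Even on the narrow reading, the adverse-event denominator is unstated.

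Other limits stand. Period-2 failures with at least one attempt are kept, and so are subjects cannulated on a later attempt, whose attempt number is recorded under 9.4. Many haematomas from failed punctures therefore remain. The expected erythema is described as remitting within minutes without treatment (9.8), and serious unexpected events are notified under 11.2.3 whatever 7.4 says.

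A reader might infer that the rule biases event rates downward overall and flatters the interventions against usual practice. The documents do not support that. Most listed deviations are under-exposure, and no between-method adverse-event comparison is planned. Excluding a subject also removes that subject's comparator period. That a subject might stay away from period 2 because of a period-1 event is possible, but nothing in the documents shows it.

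**Conclusion.** The point holds as a defect in the stated analysis set. Applied as written, 7.4 removes about 6 to 7 of 60 exposed subjects at the planned 12% loss, plus an unknown number with deviations, from the adverse-event frequencies, the CIOMS bands and the skin-type analysis. Their events are not lost from the record, since 11.2.1 requires recording and follow-up.

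The exclusions for over-long heat and failed period-1 cannulation would tend to lower the erythema and haematoma rates; the net direction over all exclusions cannot be determined. A change of band is possible, but only under assumed counts near a cut-off. The conclusion rests on reading 7.4 as general, which its wording supports, and on the plan's own loss figure. It should be corrected before analysis.

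**What to change.** State in 7.4, 11.2.1 and 14.3 that the per-protocol matrix applies to effectiveness only. State also that all adverse-event tables, the frequency categories and the skin-type analysis include every subject in whom any intervention or comparator was started. Present these by method received and by period, regardless of deviation, failed cannulation or non-attendance at period 2, and give the denominator with each frequency.

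The cost is a sentence in each section and slightly more tabulation. Events are already recorded from first application, so no new data, sample size or change in conduct is needed. The reported event rates may look less favourable.

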8. DESCRIPTION OF THE INTERVENTIONS AND THE COMPARATOR

8.1. Description of interventions

8.1.1. Application of dry topical heat:

The application will be carried out with two sacks of algarrobo seeds, joint previously heated in the microwave for 0.30 seconds at 850 W of power; 0-1 minute according to instructions for use.

Both sacs are deposited in an aligned and consecutive manner in the anatomical area that is a

candidate for venipuncture, usually antebrachial. The first sac will be located in the most caudal part, usually the wrist, and the second in a more cranial area. This is intended to enhance the venous flow from distal to proximal. Dry heat is effective at a temperature of 94 degrees Fahrenheit; an approximation to degrees centigrade has been made, 34.47 °C, put into practice, it could be set as 34-35°C (38,43).

The application of the bags should be carried out for 7 minutes in the approximate area to be punctured before applying pressure to stagnate the blood and thus collect the largest amount of venous blood in the area of interest (43).

The bags do not include any CE whose trademark is Tusacotermico ® purchased through its online website. This method is used to adapt perfectly to the anatomy of the body area in which it is superimposed, to be of low cost, approximately eight euros, and covered by cotton cloth which is a thermally conductive material.

In the dry topical heat intervention arm, stagnation pressure will be applied with the elastic tourniquet, whose pressure can not be monitored.

8.1.2. Intervention of high pressure tourniquet application:

It will be carried out with the use of the manual anaeroid sphygmomanometer. Brand QUIRUMED with CE Marking 0197. A pressure lower than systolic blood pressure will be applied, measured in millimeters of mercury (mmHg), or what is the same, although the radial pulse of each patient is still palpable (16). It should be placed 10 cm above the level to be punctured if it is in the ulnar zone; or in the lower area of the arm without exceeding the elbow in case of puncture on the back of the hand (15).

This material resource has been chosen because of its easy access in any nursing work environment and its acquisition would not have an additional cost; It would even be making its use profitable. In addition, it does not involve any teaching prior to its use because the nurses are acquainted.

8.1.3. Application intervention of both:

Heat will first be applied, as outlined above. After seven minutes, the pressure is applied with the sphygmomanometer throughout the venipuncture process until the vein that has been marked as a priori target is catheterized. As a result, the effect is simultaneous.

8.2. Temporality inherent in interventions

It has been recorded that the third method describes the duration of the minutes approximately (37). The rest is considered to have a shorter duration.

8.3. Description of the comparator

Usual practice, up to now: The steps established in the standardized and approved venipuncture guide CLSI GP41-A6 (44) have been followed. It has been taken into account, the modification of said guide by Lima-Oliveira et al. in the order of steps to follow to put on the gloves; in such a way that it adapts to the usual clinical practice in Spain (27).

Therefore, the steps of the latter, CLSI GP41-A6 (44), will be followed, allowing the gloves to be placed in the order considered by the nurses. The irrevocable condition will be to comply with this step, as well as to comply before the step corresponding to the venipuncture itself.

The usual method does not involve the application of topical heat previously, and the tourniquet corresponds to latex.

In this protocol, venipuncture will refer to the insertion of peripheral intravenous catheter, from the caudal to the cranial part of the forearm. It will be considered successful, after the insertion of the catheter, venous reflux occurs and the extraction of a basal blood sample is possible.

8.4. Justification of the comparator

The comparator corresponds to the usual clinical practice up to now, arises from the need to know new alternatives to the work method harmonized in our environment.

In particular, both the approved and standardized guide (44) and an unstandardized guide have been considered, which, based on the first one, undergo minor modifications (27). While the standardized guide comes from the United States, so the work dynamics is different, the non-standardized one emerges at the Complutense University of Madrid, at the national level; It addresses the necessary adaptation to the Spanish work dynamic (27,44).

8.5. Adherence to interventions and protocol deviations

Adherence to the protocol will be ensured with the following resources:

- The time and the power of the heat source emitted to the carob bean sacks will be carried out by means of a microwave, whose power and time will be pre-set.

- The application time of the seed bags, seven minutes, will be controlled through a portable countdown timer. There will be a countdown and ascending timer with CE marking, for each subject. The nurse will program the device so that, after seven minutes from the application of the bags, an alarm is issued to remove them. Likewise, when the alarm sounds, an ascending count begins and the time elapsed in excess can be known; in which case.

Deviations from the protocol and data retrieved will be considered in the following cases:

Application of dry topical heat

1. If the two sacks of seeds are not heated sufficiently -> It will proceed to heat two more again. There will always be two more sacks of reserve; so reheating sacks is not recommended because the temperature that could reach them is unknown and could generate "noise" to assess the effectiveness of the intervention.
2. If 7 minutes are not reached -> Protocol deviation
3. If the bags are left in excess of 7 minutes -> Protocol deviation
4. If a sack of seeds is released, or both, and recovers to its previous position in less than 1 minute (Flexibility time). No need to let act one more minute -> Data recovered.
5. If a sack of seeds, or both, comes off and does not recover to its previous position in less than 1 minute (Flexibility time) -> Protocol deviation
6. If the two sacks of seeds were detached, without the possibility of estimating the time that has elapsed approximately -> It is recovered and the process is started again.

There will be another pair of bags for the possibility of loss of them.

Application of high tourniquet pressure

1. Pressure exerted with the sphygmomanometer less than 100 mmHg is considered insufficient -> Protocol deviation
2. If the pressure of the sphygmomanometer gradually decreases due to forgetfulness of the valve fixing that controls the air output before performing venipuncture-> fix the valve. Data recovered.
3. If the pressure of the sphygmomanometer gradually decreases due to forgetfulness of the valve fixing that controls the air output after performing venipuncture-> Protocol deviation

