9.2. Workflow of Clinical Trials Unit for bioequivalence studies

In any of the bioequivalence trials, subjects are recruited who meet the inclusion and exclusion criteria added to those described above.

It supposes an income around 24 h, according to the design of each trial, and the intravenous cannulation to each subject to perform the pharmacokinetics of each drug. A recruiting visit is made to inform about the clinical trial in question, the Patient Information Sheet and the Informed Consent are delivered.

It is ensured that they do not carry any disease; the following is done:

- Blood and urine extraction. Biochemistry, Hematology, Serology and urinary sedimentation. - Vital signs. Blood Pressure (BP), Heart Rate (HR), Temperature (T).
- Anthropometry Weight, Size, Body Mass Index (BMI)
- Electrocardiogram (ECG).
- Physical exam. Concomitant treatment.

In this visit will be carried out, only the selection of subjects according to the criteria of inclusion / exclusion of the trial that takes place in the unit. Subjects enter the night before the prescribed day to perform pharmacokinetics. Next day, at 08:00 h, intravenous cannulation is started by the nursing team. The subjects remain fasting from dinner on the day of admission. The medication is always administered after the canalization and once a basal blood sample has been extracted in tubes whose additive is dipotassium ethylenediaminetetraacetic acid (K₂EDTA).

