9.4. Development of fieldwork of the trial

The first evaluation of the VIA scale (36) will be carried out, according to the number of optimal puncture points (PPO), before the application of the arm assigned by the main researcher and will correspond to the inclusion and exclusion criteria; pre-intervention assessment. This will be transcribed as the first VIA scale assessment (36).

In the interventions, the VIA scale will be evaluated twice (36). The second assessment will be carried out after the application of the intervention or randomly assigned comparator; and before performing venipuncture.

In the case of the comparator, it will only be evaluated once; It will not be assessed if it denotes a change of stage, since no intervention is applied. If this corresponds to the first period, the registration stage of the inclusion / exclusion criteria will be transcribed, if it corresponds to the second period, the corresponding nurse will assess it.

In both cases, the intervention or comparator will be applied, the success or failure in successful venipuncture will be recorded on the first attempt. In the case of failure, the attempt number to which the catheterization was possible will be recorded. Table 2

| ORGANIZATION CHART ACCORDING TO VISITS | | |
|---|-----------------|---|
| ENROLLMENT VISIT | FIRST DAY ENTRY | SECOND DAY ENTRY |
| 
 1. Information Sheet 2. Informed consent form. 3. Training for the nurses listed on the form. | X | 
 1. Subjects inclusión according to inclusión and exclusión criteria VIA assessment 2. Randomized assignment 3. Intervention/comparator assigned application. 4. Post intervention VIA assessment. 5. VAS pain assessment. 6. FITZPATRICK scale skin assessment 7. Hemolysis analysis. |

Table 2. Organization chart according to visits. Own elaboration.

This organization chart, Table 2, will be specific to the first period of the clinical trial. Another detailed organization chart has been prepared for the two study periods in section 9.7.3.

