9.8. RISKS-BENEFITS

A. RISKS

Derived from interventions

Possible local erythema due to the application of dry topical heat. They have only been registered in those individuals that denote "sensitive" skins; without being visible in "non-sensitive" skins. In addition, it has been documented that it remits after a few minutes without the need for treatment (37).

Possible transient paresthesia in the arm applied the high pressure with the sphygmomanometer because of overcoming an average blood pressure of 100 mmHg. No case has been documented

(37) although the possibility of it is considered. It is solved assuring the presence of radial pulse in mentioned upper limb.

Derived from venipuncture

Possible hematoma and pain due to the venipuncture procedure itself. As well as a vasovagal syncope. The sensation of pain due to the pressure exerted by the elastic compressor is also contemplated, whose origin is attributed to the type of material rather than the pressure exerted.

Derived from the evaluation of blood samples

No risk has been registered, neither direct nor indirect, for the observation of plasma in blood samples.

B. BENEFITS

Beneficial effects have been registered in the increase of the antebrachial venous perception, previous step to the venipuncture, with the combined application of pressure and heat (37). Therefore, it suggests a possible beneficial effect in successful intravenous cannulation in a smaller number of attempts.

No direct benefit has been recorded on the patient in observing the plasma of the blood samples. However, it could be considered that the indirect benefit would be directly related to the transcendence of the clinical findings.

A. EVALUATION OF THE RISK-BENEFIT BALANCE

As a consequence, the local erythema that remits in minutes would reflect greater benefit than the appearance of hematoma of prolonged duration to days; produced by failed intravenous lines. The transient paresthesia, with easy solution, could reduce the pain perceived by the subject, whose impact would be beneficial. Both the pain of venipuncture and vasovagal syncope occur with reduction thereof, the lower the number of attempts at venipuncture.

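### When systolic pressure is 100 mmHg or less, no cuff pressure satisfies both 8.1.2 and 8.5 item 1, so such a subject would be excluded after randomisation, and only in the two cuff groups; the number is unknown and may be zero

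*Combined protocol and SAP*

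**What the plan says.** **Upper limit.** For the high-pressure intervention, 8.1.2 states: "A pressure lower than systolic blood pressure will be applied". It then gives the bedside equivalent: "or what is the same, although the radial pulse of each patient is still palpable". The combined intervention (8.1.3) uses the same cuff after the heat.

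**Lower limit.** Section 8.5, first item on tourniquet pressure: "Pressure exerted with the sphygmomanometer less than 100 mmHg is considered insufficient -> Protocol deviation".

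**Consequence.** Under 7.4, "only the data not lost or deviations from the protocol will be included". The wording is awkward, but the same section calls this a protocol-compliance analysis and admits only those who followed the guidelines. The clear reading is that deviations are left out.

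**Who is exposed.** In the heat-only arm, "stagnation pressure will be applied with the elastic tourniquet, whose pressure can not be monitored". The comparator uses a latex tourniquet (8.3). The 100 mmHg rule therefore applies to the pressure and combined groups only.

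**Entry.** Sections 7.2 and 7.3 set no systolic minimum. Table 2 in 9.4 describes selection on the cannulation day as "Subjects inclusión according to inclusión and exclusión criteria VIA assessment". The host trial has criteria of its own, since "subjects are recruited who meet the inclusion and exclusion criteria added to those described above" (9.2), but they are not reproduced.

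**Pulse as safeguard.** Section 9.8 foresees possible transient paresthesia from the cuff, reports no documented case, and says of it: "It is solved assuring the presence of radial pulse in mentioned upper limb".

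**The concern.** The two limits are set on different scales. The upper one follows the subject's own systolic pressure; the lower one is a fixed number. For a subject with low enough pressure they cross, and nothing the nurse does is compliant. Staying under 100 mmHg is a listed deviation. Going to 100 mmHg or more breaks 8.1.2; section 8.5 does not list that, but the glossary defines a deviation broadly enough to include it.

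The heat rules in 8.5 also exclude subjects, but for how the heat was applied, which staff can control. This rule would exclude for a characteristic of the subject, after the envelope has been opened, and in two of the three intervention groups. The main objective (5.2.1) is to find the best intervention, and 14.1.3.1.2 addresses this with a logistic regression. If low systolic pressure is related to ease of cannulation, removing such subjects from the cuff groups while keeping them in heat-only would make the groups less comparable. The documents do not say which way that would work.

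**Working it through.** **1. The plan's own figure.** Section 14.1.2 gives paired proportions 0.74 and 0.95, two-sided 5%, 80% power and 12% loss, with a result of 60. Taking the two periods as independent (my assumption):

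- Discordant proportion = 0.74 × 0.05 + 0.95 × 0.26 = 0.284; difference = 0.21.
- n = [1.96 × √0.284 + 0.8416 × √(0.284 − 0.21²)]² / 0.21² = 48.1.
- With continuity correction, 48.12 + 1/0.21 = 52.9; divided by 0.88, 60.1.

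The stated 60 is reproduced to within rounding. The pairs expected after loss are 60 × 0.88 = 52.8.

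**2. Pressures that comply.** The two rules together require 100 ≤ P < systolic, so the number of whole-mmHg settings is max(0, systolic − 100).

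| Systolic (mmHg) | Compliant settings |
|---|---|
| 95 | 0 |
| 99 | 0 |
| 100 | 0 |
| 101 | 1 |
| 105 | 5 |
| 110 | 10 |
| 120 | 20 |

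The conflict is strict at 100 or less. At 101 to 105 the rules are compatible on paper, but 1 to 5 mmHg is very little to work with on a manual aneroid gauge.

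**3. Who is exposed.** Section 6.3 has four heat, four pressure and four combined envelopes, repeated five times. Cuff groups: 5 × (4 + 4) = 40. Heat-only: 5 × 4 = 20. Each group has 20, or 20 × 0.88 = 17.6 after loss. Of the 40 cuff subjects, 5 × (2 + 2) = 20 receive the cuff in the second period.

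**4. Effect of one affected subject, all after 12% loss.**

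- Pairs: 1 / 52.8 = 1.9%. The subject's comparator result goes too.
- Group success rate: removing one of n subjects moves the rate by at most 1/n = 1 / 17.6 = 5.7 points, up or down.
- Standard error at the planned 95%: √(0.95 × 0.05 / 17.6) = 5.2 points.
- In whole subjects, with 17 successes in 18 (94.4%): dropping the one failure gives 17/17 = 100% (+5.6 points); dropping a success gives 16/17 = 94.1% (−0.3 points). The maximum arises only in an extreme case, such as the excluded subject being the group's sole failure.

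**5. How many.** The share q of subjects with systolic 100 mmHg or less is not in the documents. The range below is assumed. Pairs lost = 40 × 0.88 × q = 35.2q.

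| Assumed q | Pairs lost | Pairs left of 52.8 |
|---|---|---|
| 0% | 0 | 52.8 |
| 1% | 0.4 | 52.4 |
| 5% | 1.8 | 51.0 |
| 10% | 3.5 | 49.3 |
| 20% | 7.0 | 45.8 |

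In heat-only, this rule removes nobody at any q.

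**The case against.** **Nothing shows that anyone would be affected.** The host trial screens for health, takes blood pressure at recruitment (9.2) and applies criteria we cannot see. It may already exclude such volunteers. This stands in full, and is why the effect is stated per subject.

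**The primary test is not harmed.** A whole within-subject pair is removed, so the remaining McNemar pairs are still valid. This also stands. It has been argued further that the plan has room for lost pairs, with 60 envelopes against the 54 in 2.13. That part is weak: the spare 6 is less than the expected loss of 0.12 × 60 = 7.2, and 7.4 treats losses and deviations separately.

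**The root cause is 7.4.** Excluding every deviation is what turns a wording conflict into lost data. This is true, and analysing everyone as assigned would remove the statistical part. The nurse would still have two instructions that cannot both be followed.

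**A reader might infer a safety conflict**, in which the plan pushes the nurse to inflate until the pulse disappears. The documents do not support this. Section 8.5 only classifies a reading under 100 mmHg; it never tells anyone to inflate past loss of the pulse, and 9.8 makes the pulse the safeguard. The natural outcome is an excluded subject.

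**A reader might also infer that the group comparison is biased.** That is not shown either: the count may be zero and the direction is unknown.

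**Conclusion.** The rule conflict is real and follows from the text alone. At systolic 100 mmHg or less the compliant range is empty, exclusion follows under 7.4, and this rule can act only on the 40 cuff subjects. Nothing in 7.2 or 7.3 prevents it.

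The consequence is small on what can be shown. Per affected subject it is one lost pair, plus a shift in one group's rate no larger than about one standard error. The concern is possible bias in the ranking regression, not a fault in the paired test. The sizes assume 12% loss spread evenly over the groups and the planned 95% success. How often it happens depends on host-trial criteria and a blood pressure distribution that the documents do not give. It merits a low-priority clarification.

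**What to change.** Add to 8.5, tourniquet pressure item 1:

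> If the radial pulse is lost at or before 100 mmHg, use the highest pressure at which it is still palpable and record that pressure; this is not a protocol deviation and the subject stays in the analysis in the assigned arm.

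This keeps the 100 mmHg floor wherever it can be met and follows the definition of the intervention in 8.1.2. A pulse trigger is better than a systolic cut-off. It covers the narrow zone just above 100, because the nurse need only check whether the pulse is present at 100. It also works on the day of use for the 20 subjects who get the cuff in the second period, about a week after randomisation.

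The cost is one sentence and a recorded pressure. No new blood pressure reading is required, since 8.1.2 already relies on the pulse. The downside is that a few cuff-group subjects would receive slightly under 100 mmHg.

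If the sponsor intends 100 mmHg as a true minimum dose, the alternative is an entry limit above 100 mmHg systolic in 7.2, checked before the envelope is opened and applied to all arms. That needs a reading at entry, and it would not settle the pressure in the second period.
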